9.2.12 Imaging Examinations

Upper extremity MRIs for study participants will be collected at Baseline, at 3, 6, 12 and 24 months. The Baseline (pre-operative) MRI follows standard of care imaging and will not follow the study MRI Image Acquisition Protocol. The Baseline MRI must occur within 12 months of enrollment into this study. MRI at 3, 6, 12 and 24 months post-surgery will be collected per Image Acquisition Protocol. All diagnostic images collected by the site will be modified in order to protect subject's identity and provided to an external reviewer as detailed in the Image Transfer

CONFIDENTIAL AND PROPRIETARY

Study Protocol	Smith-Nephew
A Prospective, Multi-center, Randomized Controlled	Number: REGENETEN.2020.01
Study to Evaluate the Safety and Efficacy of ARCR augmented with REGENETEN™ Bioinductive Implant	Version: 2.0, 08 Dec
System in Full-thickness Tears (large or massive) Repair	2021
versus ARCR alone	Page: 68 of 134

Protocol. The independent reviewer will be a certified radiologist selected by the Sponsor based on experience in orthopaedic imaging. The following reviewer assessments will be performed for all MRIs collected post-OP throughout the study (for endpoint analysis):

- Sugaya score
- Goutallier grading
- Total tendon thickness, tendon length
- Size of retear (anteroposterior [AP]/mediolateral [ML])
- Shape of retear

All MRI assessments are detailed in the Image Review Charter. All imaging data will be stored in electronic Digital Imaging and Communications in Medicine (DICOM) format at the site until they are no longer needed in case further evaluation by an independent centralized reviewer is requested by NMPA, PMDA, MHRA, EMA, TGA, Medsafe, HealthCanada, or FDA.

The specific imaging evaluation requirements will be provided in a separate document to radiologists.

9.3 HEALTH ECONOMICS/QUALITY OF LIFE

Health economic evidence will be collected throughout the study.

9.3.1 EQ-5D-5L Questionnaire

The EQ-5D-5L questionnaire will be collected at the pre-operative visit and at 3-, 6-, 12- and 24-months after surgery. A paper questionnaire will be provided by the Sponsor to be completed by the subject.

The EQ-5D-5L essentially consists of 2 pages: the EQ-5D descriptive system and the EQ visual analogue scale (EQ VAS).

CONFIDENTIAL AND PROPRIETARY

Study Protocol	Smith-Nephew
A Prospective, Multi-center, Randomized Controlled	Number:
Study to Evaluate the Safety and Efficacy of ARCR	REGENETEN.2020.01
augmented with REGENETEN™ Bioinductive Implant	Version: 2.0, 08 Dec
System in Full-thickness Tears (large or massive) Repair	2021
versus ARCR alone	Page: 69 of 134

The descriptive system is used to describe the subject's health state and consists of five dimensions: mobility, self-care, usual activities, pain/discomfort and anxiety/depression. Each dimension has 5 levels to choose the most appropriate answer: no problems, slight problems, moderate problems, severe problems and extreme problems. The subject is asked to indicate his/her health state by marking the most appropriate statement in each of the five areas [45].

The EQ VAS records the subject's self-rated health on a vertical visual analogue scale. The endpoints on the scale are labelled 'The best health you can imagine' and 'The worst health you can imagine'. The VAS can be used as a quantitative measure of health outcome as judged by the individual respondents.

Responses for the EQ-5D-5L Score will be recorded in the eCRF.

CONFIDENTIAL AND PROPRIETARY

Study Protocol	Smith-Nephew
A Prospective, Multi-center, Randomized Controlled	Number:
Study to Evaluate the Safety and Efficacy of ARCR	REGENETEN.2020.01
augmented with REGENETEN™ Bioinductive Implant	Version: 2.0, 08 Dec
System in Full-thickness Tears (large or massive) Repair	2021
versus ARCR alone	Page: 70 of 134

10. STATISTICAL DESIGN

A statistical analysis plan (SAP) will be written and finalized prior to database lock. The following is a brief description of the analyses to be described in this plan.

10.1 GENERAL

Smith+Nephew's Global Biostatistics group or designee will conduct the statistical analysis for this study. Unless otherwise stated, all significance tests will be two-sided, performed at the 5% significance level. Resulting p-values will be quoted. Point estimates and their corresponding 95% two-sided confidence intervals will be generated where appropriate. Where data summaries are specified, categorical or ordinal variables will be summarized with frequencies and percentages. Continuous variables will be summarized with the following summary statistics: number of observations, mean, median, standard deviation, minimum and maximum values. All analyses will be performed in SAS 9.4 (or later).

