2. SYNOPSIS

Title of Study: Study Design:	A Prospective, Multi-center, Randomized Controlled Study to Evaluate the Safety and Efficacy of ARCR augmented with REGENETEN™ Bioinductive Implant System in Full-thickness Tears (large or massive) Repair versus ARCR alone. A prospective, randomized, multi-center, controlled clinical study, 3 study arms, 24 months follow up, adaptive design with up to 300 subjects (130 ARCR augmented with REGENETEN; 130 ARCR alone and up to 40 revision repair subjects).
Study Type:	Pre-market (China), Post-market, randomized controlled trial (RCT).
Study Product:	REGENETEN Bioinductive Implant System™ is comprised of disposable instruments, a resorbable bovine collagen scaffold, poly-I/d-lactide (PDLLA) tendon anchors to secure the scaffold to the underlying tendon, and PEEK bone anchors to secure the implant to bone. REGENETEN is indicated for the management and protection of tendon injuries/rotator cuff tendon injuries (see Indications Section 4.4.1) in which there has been no substantial loss of tendon tissue.
Comparison Group(s):	Arthroscopic rotator cuff repair (ARCR) treatment alone.
Study Purpose:	To assess the safety and efficacy of ARCR augmented with REGENETEN in subjects requiring full-thickness rotator cuff tear repair or revision repair versus ARCR alone. The study results will be used to support product registration in China and post market clinical follow-up (PMCF) primary in Europe, Australia (AUS), New Zealand (NZL) and reimbursement to relevant countries.
Primary Objective:	To assess the cumulative 6 months retear rate after full thickness ARCR augmented with REGENETEN and ARCR alone.

CONFIDENTIAL AND PROPRIETARY

Study Protocol	Smith-Nephew
A Prospective, Multi-center, Randomized Controlled	Number:
Study to Evaluate the Safety and Efficacy of ARCR	REGENETEN.2020.01
augmented with REGENETEN™ Bioinductive Implant	Version: 2.0, 08 Dec
System in Full-thickness Tears (large or massive) Repair	2021
	Page: 6 of 134

Secondary Objective(s):	To assess safety and efficacy of full-thickness ARCR augmented with REGENETEN versus ARCR alone.
Other Objective(s):	To assess safety and efficacy of full-thickness ARCR augmented with REGENETEN versus ARCR alone in at-risk-groups (diabetics, smokers, hypertensive, heavy laborer, age > 65 years); To assess safety and efficacy of full-thickness ARCR augmented with REGENETEN in revision repair subject group (observational); To generate health economic evidence.

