Study to Evaluate the Safety and Efficacy of ARCR	REGENETEN.2020.01
augmented with REGENETEN™ Bioinductive Implant	Version: 2.0, 08 Dec
System in Full-thickness Tears (large or massive) Repair	2021
versus ARCR alone	Page: 10 of 134

versus Altolt alone	1			
	 Subjective shoulder value (SSV), 			
	○ EuroQol 5 Dimension 5 Level (EQ-5D-5L) Score,			
	 Patient satisfaction Questionnaire, 			
	○ Pain, Visual analog scale (VAS) Score (additionally at			
	baseline, 2 weeks, 6 weeks, 3 months and 6 months);			
	MRI Tendon Findings in ARCR augmented with			
	REGENETEN versus ARCR alone postoperatively at			
	Baseline, 3, 6, 12 and 24 months including			
	○ Sugaya score,			
	o Goutallier grading,			
	 Total tendon thickness, tendon length, 			
	○ Size of retear (anteroposterior [AP]/mediolateral			
	[ML]),			
	○ Shape of retear;			
	Outcome of Return to Work Questionnaire in ARCR			
	augmented with REGENETEN versus ARCR alone			
	(additionally at 2 and 6 weeks);			
	Cumulative duration of opioid use in ARCR augmented with			
	REGENETEN versus ARCR alone at 2 weeks			
	postoperatively;			
	Total operative time ARCR augmented with REGENETEN			
	versus ARCR alone;			
	 Sling type and mobilization time in ARCR augmented with REGENETEN versus ARCR alone. 			
Other Exploratory Endpoint(s):	To assess safety and efficacy as summarized in secondary			
	endpoints in at-risk groups (diabetics, smokers, hypertensive,			

Study Protocol	Smith-Nephew
A Prospective, Multi-center, Randomized Controlled	Number:
Study to Evaluate the Safety and Efficacy of ARCR	REGENETEN.2020.01
augmented with REGENETEN™ Bioinductive Implant	Version: 2.0, 08 Dec
System in Full-thickness Tears (large or massive) Repair	2021
	Page: 11 of 134

	heavy laborer, age > 65 years) after full-thickness ARCR augmented with REGENETEN versus ARCR alone; • To assess safety and efficacy as summarized in secondary endpoints in revision repair subject group after full-thickness ARCR augmented with REGENETEN;					
	 To collect health economic evidence in ARCR augmented with REGENETEN versus ARCR alone: 					
	 Aggregate health care utilization costs, 					
	 Number of unscheduled visits, 					
	 Reoperation rate, 					
	 Surgeon recommendation for reoperation, type of surgery, 					
	 Time of operation to time of retear, 					
	 Level of service (LOS): In the case of reoperation: How many nights did the subject spend in the hospital as a result of surgery? 0, 1, 2, 3, 4, 5, >5. 					

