10.4 EFFICACY ANALYSIS

10.4.1 Analysis of Primary Endpoint

A binary variable will be defined based on whether each patient has a Sugaya score of Type IV or V retear/recurrence. This variable will be used to present the number of retears at the 6 month post-operative visit, together with a percentage and 95% confidence interval for a single proportion (calculated using the Clopper-Pearson Exact method).

To test whether ARCR augmented with REGENETEN is superior to ARCR alone, the null hypothesis is that the retear rate of the ARCR augmented with REGENETEN group is not better than, or the same as, the retear rate of the ARCR alone group (standard of care)::

$$H_0: \mu - \mu_0 \ge 0$$

$$H_1$$
: $\mu - \mu_0 < 0$

In the stated hypothesis, μ represents the rate of retear for those patients which received REGENETEN and μ_0 represents the rate of retear for the standard of care group. A binary variable of success/failure will be created to fit a logistic model adjusting for differences in baseline characteristics.

CONFIDENTIAL AND PROPRIETARY

Study Protocol	Smith-Nephew
A Prospective, Multi-center, Randomized Controlled	Number:
Study to Evaluate the Safety and Efficacy of ARCR	REGENETEN.2020.01
augmented with REGENETEN™ Bioinductive Implant	Version: 2.0, 08 Dec
System in Full-thickness Tears (large or massive) Repair	2021
versus ARCR alone	Page: 72 of 134

As a further analysis of the primary endpoint, the time taken for retear to occur will be assessed as a survival endpoint for both treatment groups in order to compare the trend of incidence of retear over time.

Analysis will be carried out using the FAS and PP population.

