10.4.2 Analysis of Secondary Endpoints

The following secondary endpoints will be analyzed for this study:

- Retear rate at 3, 12 and 24 months post-operative will be summarized and presented as per the Primary Endpoint analysis.
- OSS, WORC/C-WORC, Constant, SSV and EQ-5D-5L PRO scores will be calculated and summarized for each visit using descriptive statistics for continuous variables, separately for the ARCR augmented with REGENETEN group and the ARCR alone (standard of care) group. Changes from baseline to each subsequent follow up visit will be similarly summarized. Repeated measures ANCOVA models will be used to assess statistical significance in the change from baseline to each time point. The null hypothesis will be that there is no difference between baseline and the respective time point. An estimate of the LS mean difference between the time points for the scores will be reported, along with the corresponding 95% confidence interval and p-value. A separate model will be used to assess statistical significance between the treatment groups at each time point. Minimal Clinically Important Differences will be assessed and presented where appropriate.
- Patient satisfaction and return to work questionnaire will be presented as number and percentage of patients who have selected each of the responses at each time point. The duration a patient has taken away from work will be summarized descriptively.
- VAS Pain score (1-100mm) will be summarized at baseline, 2 and 6 weeks, 3, 6, 12 and 24 months using descriptive statistics for continuous variables. Change from baseline to each follow up assessment will be similarly summarized and p-values will be presented.

CONFIDENTIAL AND PROPRIETARY

Study Protocol	Smith-Nephew
A Prospective, Multi-center, Randomized Controlled	Number:
Study to Evaluate the Safety and Efficacy of ARCR	REGENETEN.2020.01
augmented with REGENETEN™ Bioinductive Implant	Version: 2.0, 08 Dec
System in Full-thickness Tears (large or massive) Repair	2021
	Page: 73 of 134

- MRI analysis will be conducted by an external vendor at baseline, 3, 6, 12 and 24 months and will be presented appropriately for continuous or categorical variables.
- Opioid use will be collected each day for 2 weeks following surgery. The number of days
 of opioid use will be calculated for each patient and this will be presented descriptively for
 all patients, by treatment type (ARCR augmented with REGENETEN or ARCR alone).

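### Secondary between-arm comparisons are each tested at two-sided 5%, and the protocol gives no testing order, no adjustment and no statement that they are supportive

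*Combined protocol and SAP*

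**What the plan says.** Section 10.1 sets the level for the whole trial: "Unless otherwise stated, all significance tests will be two-sided, performed at the 5% significance level". It adds: "Resulting p-values will be quoted".

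Section 10.4.2 covers the secondary endpoints:

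- **Scores.** "OSS, WORC/C-WORC, Constant, SSV and EQ-5D-5L PRO scores will be calculated and summarized for each visit", and then "A separate model will be used to assess statistical significance between the treatment groups at each time point". Section 8.3.2 places these scores at 3, 6, 12 and 24 months after baseline.
- **Later and earlier retear.** "Retear rate at 3, 12 and 24 months post-operative will be summarized and presented as per the Primary Endpoint analysis". The primary analysis in 10.4.1 contains a descriptive part (counts, percentages, exact intervals) and an inferential part introduced by: "To test whether ARCR augmented with REGENETEN is superior to ARCR alone".
- **Pain VAS.** P-values are described for change from baseline, not for a contrast between arms.
- **Other secondary endpoints.** Satisfaction, return to work, MRI findings, opioid days, operative time and sling use are summarised, with no test named.

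The Lan-DeMets spending function in section 11 is tied to the retear hypothesis of 15% against 30%. No section names a key secondary endpoint, a testing order, a gatekeeping rule or an adjustment. The word exploratory appears only in the synopsis, as a label for the other endpoints (at-risk groups, revision group, health economics).

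**The concern.** The primary contrast has one endpoint, one time point and an alpha-spending plan. The secondary contrasts have only the section 10.1 default, applied to each separately and whatever the primary shows. With 20 or more tests, a nominally significant score at some visit is a likely chance finding even if the device does nothing. As written, the plan would not stop such a result being reported as a significant benefit, including after a failed primary.

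This matters because the results have declared uses. The synopsis and section 8.1 mention registration in China as well as post-market follow-up and reimbursement. Section 4.3 mentions only the last two. On either version, readers outside the trial team will act on the secondary results.

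**Working it through.** **The plan's own figure.** The documents state no family-wise error rate, so there is none to reproduce. The only computed figure is the sample size of 260. For 15% against 30%, two-sided 5% and 80% power, with pooled variance under the null:

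n = [1.96·√(2·0.225·0.775) + 0.842·√(0.15·0.85 + 0.30·0.70)]² / 0.15² = 121 per arm, or 242 in total.

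A Lan-DeMets O'Brien-Fleming efficacy boundary with one look at half the information raises this by a factor of 1.004, to about 244. Adding a non-binding futility boundary of the same type, which is an assumption because the plan gives no boundary, raises it by 1.056, to about 256. That is close to 260. The calculation concerns the primary contrast only and provides nothing for the secondary tests.

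**Number of tests.** Five scores (OSS, WORC/C-WORC, Constant, SSV, EQ-5D-5L) × four visits = 20 explicit between-arm tests. If retear at 3, 12 and 24 months is also tested, 20 + 3 = 23. Pain VAS and any repetition in the per-protocol set are left out.

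**Chance of at least one false significant result, no device effect on any endpoint.**

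Independent tests: 1 − 0.95^k, so 1 − 0.95^20 = 0.64 and 1 − 0.95^23 = 0.69.

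Tests with common correlation ρ, where c = 1.96, φ is the standard normal density and Φ its distribution function:

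1 − ∫ [Φ((c − √ρ·x)/√(1−ρ)) − Φ((−c − √ρ·x)/√(1−ρ))]^k φ(x) dx.

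For false results in the device's favour only, the bracket keeps just its first term. In the table, the middle columns count false results in either direction and the last two count those favouring the device.

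| ρ (assumed) | Either, 20 tests | Either, 23 tests | Device, 20 tests | Device, 23 tests |
|---|---|---|---|---|
| 0 | 0.64 | 0.69 | 0.40 | 0.44 |
| 0.3 | 0.54 | 0.58 | 0.28 | 0.30 |
| 0.5 | 0.42 | 0.45 | 0.21 | 0.23 |
| 0.7 | 0.29 | 0.31 | 0.15 | 0.15 |
| 0.8 | 0.22 | 0.24 | 0.11 | 0.12 |
| 0.9 | 0.16 | 0.16 | 0.08 | 0.08 |

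For a single test the corresponding values are 0.05 and 0.025.

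**Check against a less uniform structure.** A simulation let correlation differ between scores, between visits and between scores and retear. It gave 0.33 to 0.54 for 23 tests with within-score-family correlations of 0.5 to 0.8, and 0.63 with correlations of 0.3.

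**Expected number of false results.** 20 × 0.05 = 1.0, or 23 × 0.05 = 1.15. This does not depend on the correlations.

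**The case against.** **Section 10 is only an outline.** It says so itself, the default in 10.1 allows for exceptions, and an SAP is to follow. A reader might infer that the trial will have no multiplicity control. The documents do not support that, because the SAP is not supplied and may add it. What stands is narrower. The protocol names the items it leaves to the SAP: interim and sample-size detail, the block scheme and extra safety summaries. Multiplicity is not among them. The SAP need only be final before database lock, the study is not blinded, and a comparative interim takes place when half of the 260 subjects reach 6 months. A testing order could therefore be chosen after comparative data exist.

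**Secondary endpoints are conventionally supportive.** There is one primary endpoint and one superiority hypothesis, and nothing says a secondary result can establish efficacy or replace a failed primary. A reader might infer that the sponsor plans such a rescue, but no passage says so. Nor does the absence of an exploratory label show that the secondary endpoints are confirmatory: the label occurs only in the synopsis, and the body calls the same items other endpoints. The gap is that the protocol does not state the status of the secondary tests either way.

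**Three of the 23 tests are inferred.** The retear wording may mean only the descriptive part of the primary analysis. Section 10.4.3 uses a similar phrase for the single-arm revision group, where no between-arm test is possible. This is a fair point, so 20 is the firm count. It lowers the figures only slightly.

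**A single figure of 45% would overstate the case.** A reader might take it as a property of the plan, or as the risk of a false claim for the device. It is neither. It needs 23 tests and an assumed correlation of 0.5, and about half of those false results would favour control.

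**Conclusion.** The concern holds in limited form. The protocol plans at least 20 secondary between-arm tests, each at two-sided 5%, without an order, an adjustment or a supportive label. Each test keeps its own 5% level, and section 10.1 does not promise more. What is missing is control across the set, or a statement that none is claimed.

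With no device effect, the chance of at least one false significant result runs from 0.64 to 0.69 (independent tests) through 0.42 to 0.45 (correlation 0.5) to about 0.16 (correlation 0.9). Even the last is about three times 5%. For false results favouring the device, it is about 0.21 to 0.23 at 0.5 and 0.11 to 0.12 at 0.8. These figures assume no effect on any endpoint and a common correlation that the documents do not give. The primary conclusion and its error rate are unaffected.

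**What to change.** Amend 10.1 and 10.4.2, and carry the change into the SAP, before interim comparative data are seen:

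1. State that the confirmatory 5% level, with the group-sequential boundaries, applies to the 6-month primary contrast.
2. Allow a secondary significance claim only if the primary is significant, and only within a short fixed sequence of named endpoints and visits, stopping at the first non-significant result. The sponsor chooses the sequence and states the analysis at which each member is tested.
3. Report all other secondary comparisons with estimates, 95% confidence intervals and nominal p-values labelled exploratory.
4. Say whether retear at 3, 12 and 24 months is to be tested or only described.

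If no secondary claims are wanted, it is enough to label every secondary p-value exploratory.

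The cost is wording only, with no added patients, visits or data. The sponsor gives up significance claims on secondary endpoints outside the sequence, and on all of them if the primary fails.

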10.2 ANALYSIS POPULATIONS

The following study populations and analysis sets will be defined.

- Full analysis set (FAS): following the Intention to Treat principle including all randomized patients who were recruited into the study and attended at least one post-surgery assessment. This analysis population includes all randomized patients in the groups to which they were randomly assigned, regardless of their adherence with the entry criteria, regardless of the treatment they actually received, and regardless of subsequent withdrawal from treatment or deviation from the protocol.
- Per protocol set (PP): including all patients in the full analysis set who have no significant protocol deviations and met the inclusion/exclusion criteria.
- Safety analysis set (SAF): including all patients who have received the study device.

CONFIDENTIAL AND PROPRIETARY

Study Protocol	Smith-Nephew
A Prospective, Multi-center, Randomized Controlled	Number:
Study to Evaluate the Safety and Efficacy of ARCR	REGENETEN.2020.01
augmented with REGENETEN™ Bioinductive Implant	Version: 2.0, 08 Dec
System in Full-thickness Tears (large or massive) Repair	2021
	Page: 71 of 134

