5.2 SECONDARY OBJECTIVE(S)

To assess safety and efficacy of full-thickness ARCR augmented with REGENETEN versus ARCR alone.

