6.1.2 Comparator Treatment

Arthroscopic rotator cuff repair (ARCR) alone.

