7.6 ENROLLMENT

Every subject that has signed consent, met inclusion/exclusion criteria, and received either ARCR augmented with REGENETEN or ARCR alone will be considered enrolled in the study.

In the event that a subject has a sequential bilateral ARCR augmented with REGENETEN or ARCR alone, both shoulders treated after informed consent can be enrolled in the study.

A subject that has been randomized into the ARCR augmented with REGENETEN arm and with a diagnosis of a recurrent large or massive tear will not be enrolled into the revision repair subject group. However subjects that were randomized into the ARCR alone arm can be enrolled into the revision repair subject group in case of recurrent large or massive tears.

Subjects that provided informed consent but do not receive the study treatment for any reason will be considered as screen failure.

CONFIDENTIAL AND PROPRIETARY

Study Protocol	Smith-Nephew
A Prospective, Multi-center, Randomized Controlled	Number:
Study to Evaluate the Safety and Efficacy of ARCR	REGENETEN.2020.01
augmented with REGENETEN™ Bioinductive Implant	Version: 2, 08 Dec 2021
System in Full-thickness Tears (large or massive) Repair versus ARCR alone	Page: 42 of 134

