7.8 WITHDRAWAL

7.8.1 Withdrawal from Treatment

Subjects may be withdrawn from having the study device implanted at a date close to surgery or during surgery for the following reasons:

- At the discretion of the Investigator due to:
 - A change in treatment being clinically warranted
 - An adverse event
 - Any other significant reason identified by the Investigator.

If at any point during the study, the study device needs to be revised for any reason intraoperative data from the reoperation will be collected according to the Reoperation Case Report Form (CRF).

Reoperation cases will not be enrolled into the revision repair subject group if the subjects has been randomized previously into the ARCR augmented with REGENETEN arm. However subjects that have been randomized into the ARCR alone arm can be enrolled into the Revision Repair subject group.

CONFIDENTIAL AND PROPRIETARY

Study Protocol	Smith-Nephew
A Prospective, Multi-center, Randomized Controlled	Number:
Study to Evaluate the Safety and Efficacy of ARCR	REGENETEN.2020.01
augmented with REGENETEN™ Bioinductive Implant	Version: 2, 08 Dec 2021
System in Full-thickness Tears (large or massive) Repair versus ARCR alone	Page: 43 of 134

Following reoperation subjects shall continue to have follow-up visits in order to monitor the subject's health status only. Potential data following the reoperation will not be included as study data but presented separately as safety data.

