10.5 SAFETY ANALYSES

All safety endpoints will be summarized using the safety population.

Adverse Events

The number of subjects reporting: adverse events, serious adverse events, adverse device effects, serious adverse device effects, and unanticipated serious device effects will be summarized. In addition, for each adverse event, the following will be summarized: severity, the relationship to investigational device use, outcome and duration of the resolved adverse events and the duration of the adverse events at trial discontinuation.

Device deficiencies

The number of device deficiencies and the number of patients reporting a device deficiency will be summarized as well as a summary of device deficiencies with the potential to cause SADE.

Additional summaries of safety endpoints, if applicable, will be described in the SAP.

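### The safety analysis set admits only recipients of the implant, so ARCR-alone subjects treated as assigned fall outside the planned AE and SAE summaries

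*Combined protocol and SAP*

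**What the plan says.** Section 10.2 sets out three analysis sets. The third is the "Safety analysis set (SAF): including all patients who have received the study device". Section 10.5 then states: "All safety endpoints will be summarized using the safety population". It lists counts of subjects with AEs, SAEs, device effects, serious device effects and unanticipated serious device effects, followed by device deficiencies. What it leaves to the SAP is limited: "Additional summaries of safety endpoints, if applicable, will be described in the SAP".

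The secondary objective in section 5.2 is comparative: "To assess safety and efficacy of full-thickness ARCR augmented with REGENETEN versus ARCR alone". Section 6.1.2 gives the comparator as "Arthroscopic rotator cuff repair (ARCR) alone". Under section 7.6, eligible, consented subjects who "received either ARCR augmented with REGENETEN or ARCR alone will be considered enrolled in the study". Section 8.3.4 makes all AEs from enrolment onward a safety endpoint, without restriction by arm.

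**The concern.** The safety set is defined by exposure to the implant, and a control treated as assigned never has that exposure. The plan therefore collects control-arm adverse events but names no set in which to summarise them. Section 4.4.4 lists infection, nerve damage and persistent stiffness among the complications of the surgery itself, so both arms carry those risks. A table confined to device recipients would show how often such events occurred after augmented repair, with no concurrent rate after repair alone. Any added risk from the implant could not be read from it, and that is the comparison section 5.2 asks for.

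**Working it through.** The documents state no size for the safety set, so there is no figure to reproduce. The check is a reading of definitions followed by a head count.

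**Step 1: what the study device is.** The synopsis names the REGENETEN Bioinductive Implant System as the study product. Section 7.8.1 uses the term for something implanted: "Subjects may be withdrawn from having the study device implanted at a date close to surgery or during surgery". Where the protocol means the treatment of either arm, as in section 7.6, it names both or speaks of study treatment. Section 10.2 uses the narrower term.

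**Step 2: whether another set covers controls.** Section 10.4.1 assigns the FAS and PP sets to the primary efficacy analysis. Section 10.5 names only the safety population. No section widens that population or plans an AE summary for controls.

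**Step 3: head count.** Inputs are 130 subjects per randomised arm (section 11) and up to 40 revision subjects (section 7.1), all treated with REGENETEN and not randomised (section 8.2.1). Let c be the number of controls who receive the device, through crossover, entry to the revision group or a second enrolled shoulder. The documents give no value for c.

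- Controls outside the set = 130 − c. With all treated as assigned, c = 0, so 130 of 260 randomised subjects, 130/260 = 50%.
- Set as written, c = 0: 130 + 0 + up to 40 = up to 170 of 300 subjects, 170/300 = 56.7%.
- Set defined by study surgery: 130 + 130 = 260 of 260 randomised subjects, or up to 300 with the revision group.

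If c exceeds zero, the added subjects are in the set because they received the device. They do not form a control group.

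**Step 4: which tables can properly be limited to device recipients.** Table 12.1-1 heads the ADE and SADE column as covering relation to the device or to the procedure. The opening sentence of section 12.1.2 is narrower (use of the investigational product), but its relatedness categories again include the procedure. On the table's wording, a procedure-related infection in a control is an ADE or SADE. Limiting all device-effect tables to device recipients would drop that event in one arm and count it in the other. Section 12.3 has investigators assess relationship to device and to procedure for every AE, so the two can be tabulated separately from data already collected.

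**Step 5: basis for the new set.** Enrolment under section 7.6 requires that the eligibility criteria were met. A set built on that definition plus every device recipient would keep an ineligible implanted subject and leave out an equally ineligible treated control. Basing the set on surgery performed treats both arms alike.

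**Step 6: cross-reference.** Section 10.4.3 sends safety in the revision and at-risk groups to the secondary endpoint analysis. Section 10.4.2 contains no AE analysis, so the reference leads nowhere.

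**The case against.** The strongest reply is that this is a drafting slip the SAP will cure. Section 10 calls itself a brief description, the term study device has no entry in the abbreviations and definitions list, and section 7.8.1 moves from revising the study device to reoperation cases from both arms, which suggests loose use. Control AEs are collected, so the tables can be produced at any time before lock. Reoperation rate and unscheduled visits are compared between arms in section 8.3.3, outside the safety set.

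Much of this stands, and it limits the severity. It does not remove the defect. The implant reading is the natural one, a SAP that follows section 10 would carry the definition forward, no SAP text is in the documents reviewed, and section 10.5 defers only further summaries where applicable. Reoperations and visits do not replace AE and SAE rates.

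Two stronger readings are tempting. A reader might infer that an interim safety table would omit about half of the first 130 subjects. Sections 8.1, 10.6 and 11 plan an interim on relative performance, sample size and stopping for efficacy or futility, with no safety analysis. Only an example in section 12.5.1, about listing ongoing events, hints at one. A reader might also infer that revision subjects would be pooled with randomised device subjects, up to 40 of 170 (23.5%). That is set membership only. Section 10.4.3 plans to present safety for the revision group as such, and no section states a pooled table.

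**Conclusion.** The plan is wrong as written and should be fixed. Sections 10.2 and 10.5 together leave ARCR-alone subjects treated as assigned, 130 of 260 planned randomised subjects, outside the planned AE and SAE summaries, against the comparative safety objective in section 5.2. The count assumes full recruitment, no control receiving the device, and that study device means the implant. It describes membership of a set and is not an effect on any result.

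A reader might go further and infer that the safety objective is lost or the trial's conclusion compromised. The documents do not support that: the safety analysis is descriptive with no hypothesis test, control-arm events are recorded, and the primary analysis uses other sets.

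**What to change.** - **Section 10.2:** define the safety set as all subjects who underwent study surgery (ARCR with or without REGENETEN), including those with eligibility deviations, analysed by treatment received.
- **Section 10.5, layout:** present AEs, SAEs and procedure-related events for the two randomised arms side by side, with the non-randomised revision group in a separate column.
- **Section 10.5, device tables:** limit to device recipients only the REGENETEN device-deficiency tables and the events attributed to the implant itself. Tabulate procedure-related ADEs and SADEs in both arms, with relationship to device and relationship to procedure shown separately.
- **Events after reoperation or revision-group entry:** present these separately, consistent with section 7.8.1: "Potential data following the reoperation will not be included as study data but presented separately as safety data".
- **Section 10.4.3:** point the revision-group and at-risk safety summaries to section 10.5.

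The cost is short text changes in these sections and matching SAP text, through the amendment process in section 15, with ethics and authority approval as applicable. No new data are needed and the primary analysis does not change.
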